Endpoints	For this proof of concept study, the primary endpoints will be changes in Vibration Perception Threshold and Quantitative Sensory Testing between baseline and end of treatment. Secondary endpoints will be changes in nerve conduction velocity (NCV) of the sural nerve and amplitude from baseline to end of treatment, changes in Skin Perfusion Pressure (SPP) from baseline to end of treatment, change in Pain Intensity using the 11-point Numeric Pain Rating Scale (NPRS) from baseline to end of treatment, change from baseline in Brief Pain Inventory (BPI) and Brief Fatigue Inventory (BFI), change from baseline in Patient Global Impression of Change (PGIC), change from baseline in Hospital Anxiety and Depression Scale (HADS), and changes from baseline in neuropathy and foot ulcer specific quality of life instrument (NeuroQoL).
	Safety will be assessed through review of Adverse Event (AE) reports and concomitant treatments and medications. All concomitant drug or non-drug treatments used during the study will be recorded. Safety outcomes will be assessed at the interim visits and the end of study visit.
Study Procedures	Following informed consent and assessment of eligibility, subjects will complete Section A-History of the Michigan Neuropathy Screening Instrument (MNSI) with Section B- Physical Assessment completed by the site. A measurement of the depth of the right foot will be measured from the most inferior aspect of the medial malleolus to the plantar aspect of the foot when residing on the treatment pad. The depth should not be more than 8cm for eligibility. A finger stick will be performed on the subject to obtain a baseline HbA1c value (A1C Now [®] test kit) and subjects will complete a Urine Drug Screen in office. Subjects will undergo the Ankle-Brachial Index (ABI), Venous Insufficiency Assessment, and Pain Phase evaluation (at least 10 subjects in each of the 2, 3, and 4 pain phases will be enrolled). For subjects of child bearing potential a urine pregnancy test will be obtained.

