be performed on the safety analysis set, defined as all subjects who were enrolled into the study and issued study devices during the Induction Phase and followed through the Randomized Withdraw Phase . Once the subject is determined to be eligible, the subject will be issued active treatment devices and the subject will be formally enrolled into the study and become part of the Safety Analysis Set .
All recorded data will be listed by subject and time point. Descriptive statistics will be tabulated for all randomized subjects for the change from baseline to study day 120 (Completers Analysis Set), and separately for the change from baseline to the last recorded set of evaluations (End of Study Evaluation Set). This latter set should include all subjects who were randomized and complete at least one set of evaluations after randomization.
Treatment-emergent adverse events will be summarized by type, frequency, severity, and relationship to the study device. Adverse events will be provided in a listing.

Ι.	INTRODUCTION AND BACKGROUND	17
II.	STUDY OBJECTIVES	23
III.	STUDY DESIGN	24
Α.	Study Design	24
В.	EFFICACY ENDPOINTS	26
C.	SAFETY EVALUATION	26
D.	ELIGIBILITY CRITERIA	26
1.	Inclusion Criteria	
2.	Exclusion Criteria	27
Ε.	RECRUITMENT	29
F.	RANDOMIZATION	29
G.	DEVICE DESCRIPTION	29
1.	Control Unit	29
2.	Disposable Applicator Covers	
З.	Treatment Applicator	
Н.	LOGISTICS AND DEVICE ACCOUNTABILITY	
١.	LABELING	31
J.	Preparation and Administration	32
К.	Blinding	
L.	Study Assessments	
1.	Primary Efficacy Assessments	
2.	Secondary Efficacy Assessment	
З.	Exploratory Efficacy Assessment	35
4.	Additional Study Assessments	35
5.	Safety Assessments	
IV.	STUDY PROCEDURES	
Α.	VISIT 1 – SCREENING VISIT (DAY -14 TO 0)	
В.	VISIT 2 – ENROLLMENT VISIT (DAY 0)	
C.	Day 3 Phone Call (Day 3 +2 Days)	
D.	Day 15 Interim Visit (Day 15 + 3 Days)	
Ε.	Day 30 Interim Visit (Day 30 + 3 Days)	
F.	Day 45 Interim Visit (Day 45 + 3 Days)	40
G.	Day 61 Visit (Day 61 +3 Days)	40
Н.	Day 75 Interim Visit (Day 75 + 3 Days)	41
١.	Day 91 Visit (Day 91 +3 Days)	41
J.	Day 105 Interim Visit (Day 105 + 3 Days)	42
К.	Day 121 Visit (Day 121 + 3 Days)	42
L.	TREATMENT ADHERENCE/STUDY COMPLIANCE	43
M.	PROTOCOL ADHERENCE	43
N.	CONCOMITANT MEDICATIONS	43

1.	Allowed Medications
2.	Prohibited Medications/Treatments
v .	WITHDRAWAL PROCEDURES45
VI.	STATISTICAL CONSIDERATIONS
Α.	INDUCTION PHASE / BASELINE EVALUATIONS
В.	Randomized Withdraw Phase
C.	SUMMARIZATION OF RESULTS

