- Request for withdrawal by the subject for reasons other than an intolerable AE.
- Lost to follow-up, as determined by failure to respond to at least 2 telephone calls followed by certified letter sent to the subject's last known address. All attempts to contact the subject must be documented in the subject's source documents.

VI. STATISTICAL CONSIDERATIONS

The statistical analysis of the study is described in detail in a separate version-controlled prospective Statistical Analysis Plan (SAP). However, the statistical methodology described in this section of the protocol will be the basis for the detailed SAP.

This bi-phasic design includes 2 sequential periods: the *Induction Phase* and *Randomized Withdraw Phase*. All safety analyses will be performed on the *Safety Analysis Set*, defined as all subjects who were enrolled into the study and issued study devices during the *Induction Phase* and followed through the *Randomization Withdraw Phase* or until they withdraw. Once a subject is determined to be eligible, the subject will be issued active treatment devices and the subject will be formally enrolled into the study and become part of the *Safety Analysis Set*. Where not otherwise specified, the last pre-treatment observation will be used as baseline for calculating post-treatment changes from baseline.

A. Induction Phase / Baseline Evaluations

Prior to study treatment, subjects will complete the baseline health economic questions, including the Brief Pain Inventory (BPI), Brief Fatigue Inventory (BFI), Hospital Anxiety and Depression Scale (HADS), and the NeuroQoL. Vibration Perception Threshold (VPT), Quantitative Sensory Test (QST) and Nerve Conduction Velocity (NCV) will be completed. Skin Perfusion Pressure

(SPP) will be performed to obtain a baseline value of the plantar and dorsal aspect of the right foot. Once the subject is determined to be eligible, the subject will be issued active treatment devices and the subject will be formally enrolled into the study and become part of the *Safety Analysis Set*.

Subjects in the *Safety Analysis Set* will be instructed in the use of the devices for 60 days in the home environment. At Days 15 and 45, subjects will return to the clinic to have the VPT and QST conducted. Subjects will return to the clinic at days 30 and 61 for evaluation and complete questionnaires.

B. Randomized Withdraw Phase

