Randomization of subjects can occur at different times, depending on when the subject is determined to be a responder. Once a subject is determined to be a responder (based upon a 1-point decrease in average pain score over the last 24 hours using the NPRS), the subject will return the active devices and be randomized 1:1 to receive active treatment or inactive sham devices and be instructed to treat through study day 120. If a subject is determined to not be a responder at Day 91, i.e., their final chance to be randomized, the subject will be terminated from the study at the end of the Day 91 visit.

C. Summarization of Results

The tabulations will be based on the paired results for the change from the baseline to study day 120 for patients who are randomized, and separately for the last observation. Supportive subject data listings will be sorted and presented by subject number, visit date and relative study day. Listings will also include the number of days relative to the initiation of treatment. Two sets of analyses will be generated; summary tabulations for all randomized subjects who complete the baseline and study day 120 evaluations (*Completers Analysis Set*), and all randomized subjects using the baseline and last recorded set of evaluations (*End of Study Evaluation Set*). This latter set should include all subjects who were randomized and complete at least one set of evaluations after randomization.

Specific algorithms will be described in the Statistical Analysis Plan for imputing missing or partially missing dates, if deemed appropriate, under specific data topics. Imputed or derived data will be flagged in the individual subject data listings. Imputed data will not be incorporated into any raw or primary datasets. The imputed data will be retained in the derived / analysis datasets.

The total duration for a subject *on-study* will be calculated as the difference between the date of initial study treatment in the *Induction Phase* and the last day of observation plus 1 day. All calculations for defining the duration on-study will follow the algorithm DURATION = [STUDY COMPLETION OR WITHDRAW DATE – INITIAL TREATMENT DATE + 1].

Summary statistics will consist of the count and percentage in each level for categorical variables, and the sample size (n) mean, median, standard deviation (SD), minimum, and maximum values for continuous variables. All mean and median values will be formatted to one more decimal place

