than the measured value. Standard deviation values will be formatted to two more decimal places than the measured value. Minimum and maximum values will be presented with the same number of decimal places as the measured value. The number and percentage of responses will be presented in the form XX (XX.X%). Pairwise differences between the treatment groups will be calculated and 95% confidence intervals constructed.

While no formal hypothesis testing is planned, probability values may be generated to determine the magnitude of the difference between subject groups for an endpoint. All p-values that round to 0.0000 will be presented as '<0.0001' and p-values that round to 1.0000 will be presented as '>0.9999'. P-values <0.05 will be discussed as being statistically significant.

All summary tables will include the analysis population sample size (i.e., number of subjects). Study Day 1 is defined as the day the subject receives their initial exposure to the active study device. All *study days* are determined relative to the day of initial treatment with the study device. Baseline values will be defined as those values recorded closest to, but prior to, the first active study treatment during the initial phase of the study. Date variables will be formatted as DDMMMYYYY for presentation. Where appropriate, only the measurements from the right foot will be used in the calculations.

D. Adverse Events

All summaries of adverse events will be based on treatment-emergent adverse events. Adverse events will be provided in a listing. The number and percentage of subjects experiencing adverse events will be summarized. Summaries by maximum severity and relationship to the study device (active or sham) will also be provided. Serious adverse events and adverse events leading to discontinuation from the study will be presented. Treatment-related adverse events will be defined as adverse events with investigator assessment of related or possibly related. In summaries of adverse events by severity and relationship to study device, patients reporting multiple episodes will be counted once under the worst severity and the strongest relationship, respectively. Serious adverse events will also be presented by relationship to treatment. The number of patients with at least one adverse event will be tabulated for each treatment group. The number of adverse events for each treatment group will also be tabulated.

E. Sample Size

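### Section VI.C measures the arms' change from the pre-induction Day 0 value and names no covariate, leaving the randomisation-visit VPT and QST values unused in the comparison

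*Combined protocol and SAP*

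**What the plan says.** The Endpoints section of the synopsis states that "the primary endpoints will be changes in Vibration Perception Threshold and Quantitative Sensory Testing between baseline and end of treatment". Section VI gives a default rule, "Where not otherwise specified, the last pre-treatment observation will be used as baseline for calculating post-treatment changes from baseline", and VI.C repeats it: "Baseline values will be defined as those values recorded closest to, but prior to, the first active study treatment during the initial phase". No other baseline is specified anywhere in Section VI.

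For the analysis, VI.C says "The tabulations will be based on the paired results for the change from the baseline to study day 120 for patients who are randomized", with a second tabulation to the last observation. The arm comparison is a single sentence, "Pairwise differences between the treatment groups will be calculated and 95% confidence intervals constructed", and no model or covariate is named. VI.C also allows p-values and will describe those below 0.05 as statistically significant. For data between Day 0 and the end of study, the statistical paragraph of the synopsis says "All recorded data will be listed by subject and time point" and then "Descriptive statistics will be tabulated for all randomized subjects for the change from baseline to study day 120".

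A separate SAP is mentioned but was not among the documents reviewed. Section VI says that "the statistical methodology described in this section of the protocol will be the basis for the detailed SAP".

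**The concern.** In a randomised withdrawal design the arms are treated alike until randomisation. Here that covers the whole active induction, which ends at Day 61, 75 or 91. Only what happens afterwards differs by allocation. Section III.L.1 schedules VPT and QST at all three possible randomisation visits, and the visit lists in IV.G to IV.I place both tests first, before the device swap. Treatment is self-administered at home. Every randomised subject who completes the visit therefore has a VPT and QST value from before any use of the randomised device.

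Leaving that value out has two costs:

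- **Precision.** Variation between subjects in induction response stays in the change score as noise, although a measurement that could remove much of it has been taken.
- **Reading of the tables.** Change from Day 0 by arm adds induction response to post-randomisation change. A sham arm that worsens after withdrawal can still show net improvement.

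The arm difference in VPT and QST is the only randomised evidence on the primary endpoints, and it comes from at most 40 subjects. Interval width largely decides what the trial can show.

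**Working it through.** **No plan figure to reproduce.** Section VI.E calls 40 a convenience sample with no power claim, and gives no effect size, SD or correlation. The sizes below are conditional on assumptions.

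**Inputs from the documents.** Allocation is 1:1 (III.F). The synopsis describes up to 40 both as randomised and as enrolled, so fewer than 40 may be randomised. I use N = 40, and N = 24 as an assumed smaller case.

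**Assumed inputs.** Equal variances, set to 1. r0 = correlation of Day 121 with Day 0; r1 = Day 121 with the randomisation visit; r01 = Day 0 with the randomisation visit.

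**Formulas.**

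- Change from Day 0: variance 2(1 − r0); half-width = t(N−2) × √[2(1 − r0) × 4/N].
- ANCOVA on both values: V = 1 − (r0² + r1² − 2·r0·r1·r01)/(1 − r01²); half-width = t(N−4) × √[V × 4/N × (N−3)/(N−5)]. The last factor is the cost of estimating two covariate slopes.

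**Worked case, N = 40, all correlations 0.8.**

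- Change score: √(0.40 × 0.1) = 0.200; × 2.024 = 0.405 SD.
- ANCOVA: V = 1 − (1.28 − 1.024)/0.36 = 0.289; √(0.289 × 0.1 × 37/35) = 0.175; × 2.028 = 0.354 SD.
- Narrowing: 1 − 0.354/0.405 = 12.5%.

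**Other settings by the same formulas:**

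| r0 / r1 / r01 | Narrower, N = 40 | Narrower, N = 24 |
|---|---|---|
| 0.7 / 0.7 / 0.7 | 13.5% | 11.2% |
| 0.8 / 0.8 / 0.8 | 12.5% | 10.1% |
| 0.9 / 0.9 / 0.9 | 11.6% | 9.2% |
| 0.7 / 0.8 / 0.8 | 21.3% | 19.2% |
| 0.64 / 0.8 / 0.8 (serial decay, r0 = r01 × r1) | 27.2% | 25.2% |
| 0.6 / 0.8 / 0.7 | 31.2% | 29.4% |
| 0.8 / 0.6 / 0.7 | 2.7% | 0.1% |
| 0.9 / 0.7 / 0.8 | 0.1% wider | 2.8% wider |
| 0.9 / 0.8 / 0.9 | 0.3% wider | 2.9% wider |

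The last three rows are cases where Day 0 is the better predictor.

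**Why both covariates.** With the randomisation-visit value alone the variance is 1 − r1². At r0 = 0.8 and r1 = 0.6 that is 0.64, against 0.40 for the change score, and the interval is 28% wider at N = 40 and 30% wider at N = 24. Keeping Day 0 in the model protects against this.

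**Bias check by simulation.** With a true difference of 0.40 SD and 10,000 trials per setting, mean estimates were 0.389 to 0.410 and interval coverage 0.945 to 0.955 for both methods. The planned estimate is not biased, because the shared induction change cancels.

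**Mixing of phases.** The nominal shares of treatment time spent on active induction are 60/120 = 50%, 74/120 = 62% and 90/120 = 75%. The +3-day visit windows can add 3/120 = 2.5 points to each. These are shares of time, not of effect. As an illustration, suppose induction changes both arms by −0.50 SD (improvement) and sham then loses 0.40 SD. Change from Day 0 is −0.50 on active and −0.50 + 0.40 = −0.10 on sham. The difference of −0.40 is right, but the sham row still shows improvement.

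**The case against.** The strongest reply is that no error has been shown. Change from Day 0 is the declared endpoint, the arm difference is unbiased, and the study is proof of concept with no formal testing. All of that stands and limits the weight of the point. It does not remove it, because the plan promises 95% confidence intervals and will call p-values below 0.05 significant. The endpoint is also kept: with Day 0 as a covariate, ANCOVA on the Day 121 value and ANCOVA on change from Day 0 give the same arm difference.

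Second, the separate SAP may already adjust. Section VI leaves room for another baseline and does not say the differences are unadjusted. What can be shown is silence, in the section that is the SAP's stated basis. If the SAP adjusts, one sentence in VI.C settles the matter.

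Third, the gain rests wholly on assumed correlations, and 24 is not a documented number. This stands. With still fewer randomised the balance worsens. At N = 16 the half-width ratio is √[(V/2(1 − r0)) × 13/11] × 2.179/2.145. That gives about 5 to 7% narrower at equal correlations of 0.7 to 0.9, but 4% wider at 0.8/0.6/0.7 and 7% wider at 0.9/0.7/0.8. The calculation also uses one r1 for everyone, although the gap from randomisation to Day 121 is nominally 60, 46 or 30 days.

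Fourth, two VPT sites and two thermal tests in two analysis sets make eight comparisons. The plan as written already has those eight; covariates add none.

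**Conclusion.** The point holds as a cheap improvement of minor to moderate weight. Section VI takes its baseline from before induction, names no covariate, and gives the randomisation-visit VPT and QST values no stated use in the arm comparison. The cost is precision and interpretability, not bias.

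If the randomisation-visit value predicts Day 121 at least as well as Day 0 does, the settings tabulated give intervals about 12 to 31% narrower at 40 randomised and 9 to 29% narrower at 24. If Day 0 predicts better, the gain is about nil at 40, and at 24 the interval may be up to about 3% wider. These figures assume equal variances, normal data and the stated correlations, none of which the documents supply. So precision is probably, not certainly, lost. The mixing of induction and withdrawal in each arm's change follows from the design and needs no such assumption.

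**What to change.** In VI.C, and in the SAP built on it:

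1. Estimate the Day 121 arm difference for VPT (each site) and QST (heat, cold) by ANCOVA with two covariates: the Day 0 value and the randomisation-visit value taken before the device swap. Report the adjusted difference with its 95% confidence interval. Use the same model for the last recorded value in the End of Study Evaluation Set.
2. Add randomisation visit (61/75/91) as a factor in a sensitivity analysis only. III.F describes permuted blocks without stratification by visit. In simulation, with assumed visit splits of 24/8/8 and 14/5/5, the factor cost a further 1.5 to 3 points of narrowing at 40 and 3 to 6 at 24.
3. For SPP, BPI, BFI and HADS, use Day 0 and the last value at or before randomisation: Day 61 for SPP, and Day 61 or 91 for the questionnaires. For NCV and NeuroQoL, measured only at Day 0 and Day 121, adjust for Day 0. State the covariates for NPRS pain intensity too, since it is collected at Day 0 and at the visit that triggers randomisation.
4. Keep change from Day 0 as a descriptive table, split into induction and withdrawal phases.
5. State that the randomised contrast estimates continuing versus stopping PEMF after induction.

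The cost is wording, with no new visit or measurement. The main model spends two degrees of freedom. It should be fixed before unblinding, so that the choice of baseline cannot be made after seeing the results.

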	• is definitely not associated with the study device administered and is readily explained by other events or diagnoses.						

Each AE will also be independently judged by the investigator in terms of severity. The following definitions will be used for these severity assessments.

Mild:	The event is transient (<48 hours) or causes mild discomfort; no medical intervention/therapy is required				
Moderate:	The event results in mild to moderate limitation in activity – some assistance may be needed; no or minimal medical intervention/therapy is required				
Severe:	The event results in marked limitation in activity, assistance is usually required; medical intervention/therapy is required and hospitalization is possible				

Each AE will also be independently judged by the investigator in terms of seriousness. A serious adverse event (SAE) is defined as any untoward medical occurrence that:

- Results in death, or
- Is life-threatening,

Note: The term "life-threatening" in the definition of "serious" refers to an event in which the subject was at risk of death at the time of the event; it does not refer to an event which hypothetically might have caused death if it were more severe.

- Requires inpatient hospitalization or prolongation of existing hospitalization,
- Results in permanent impairment of a body function or permanent damage to a body structure,
- Is a congenital anomaly/birth defect,
- Necessitates medical or surgical intervention to preclude any one of the outcomes listed in this definition.

All SAEs must be reported *immediately* (within 24 hours of knowledge of the event) by telephone and fax to the following:

Sponsor Medical Contact – [name], MD; Regenesis Biomedical Inc.

[contact]; [contact]; [contact]

The investigator will follow up with a written description of the SAE submitted to the sponsor within 3 days, including the results of the SAE investigation and any treatment(s) provided.

All adverse events will be followed until resolution or until the investigator assesses the subject's status has returned to normal.

B. Anticipated Adverse Device Effects Associated with Provant Therapy System

Anticipated adverse events associated with PROVANT[®] Therapy System² and the procedures and medicines used in the study are as follows:

- Device fails to operate
- Warmth or burning at treatment site
- Skin reaction at treatment site (tingling, pins-and-needles, rash, blisters, swelling, dry skin, redness, numbness)

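### Any event under 48 hours that requires no intervention meets the Mild definition whatever its intensity, so the grades overlap and the severity summaries can understate severity

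*Combined protocol and SAP*

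**What the plan says.** Section X.A gives severity grading to the investigator ("Each AE will also be independently judged by the investigator in terms of severity") and supplies three definitions to be used:

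- The lowest grade, Mild, reads: "The event is transient (<48 hours) or causes mild discomfort; no medical intervention/therapy is required".
- The middle grade, Moderate, rests on a mild to moderate restriction of activity, possibly with a need for help. It covers events that call for minimal treatment and also events that call for none.
- The top grade, Severe, rests on marked restriction of activity and states that treatment is needed, with admission to hospital a possibility.

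The grades are used in three places. Section III.C plans a tabulation of incidence by maximum reported severity. Section VI.D states: "Summaries by maximum severity and relationship to the study device (active or sham) will also be provided". Section IX names the severity or incidence of adverse events among the grounds for suspending the investigation, without setting a grade threshold.

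The only rule that ranks grades is in Section VI.D: "patients reporting multiple episodes will be counted once under the worst severity and the strongest relationship, respectively".

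**The concern.** The scale mixes two axes. Moderate and Severe are set by how far the event limits activity, while Mild can be reached through duration alone. A brief but limiting event can then be placed in the lowest grade without departing from the text.

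This bears on the device under study. The anticipated effects in Section X.B include local warmth or burning, muscle cramps, headache and nausea. Such events may be short and may resolve without treatment, although the documents give no durations. For short events of this kind the duration limb can decide the grade. At stake is whether the severity summaries describe what subjects experienced, and whether investigators at up to 4 sites would grade the same event alike.

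**Working it through.** The documents give no adverse event rates or durations, so there is no figure to reproduce. The check applies the three definitions to combinations of duration, effect and need for intervention. I read the no-intervention condition as attaching to both limbs of Mild, which is the narrower reading and the kinder one to the protocol.

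Events for which no intervention is required:

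| Effect | Under 48 hours | 48 hours or longer |
|---|---|---|
| Mild discomfort, no limitation | Mild | Mild |
| More than mild discomfort, no limitation | Mild (duration limb only) | No grade |
| Mild to moderate limitation | Mild and Moderate | Moderate; also Mild if discomfort is mild |
| Marked limitation | Mild only | No grade, unless discomfort is mild |

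1. *Mild to moderate limitation, under 48 hours.* The duration limb satisfies Mild. The limitation satisfies Moderate. The intervention condition does not separate the two, because Moderate also admits events needing none.
2. *Marked limitation, under 48 hours.* The duration limb satisfies Mild. The limitation exceeds what Moderate describes. Severe fails because it states that intervention is required. The most limiting effect in the table is left with only the lowest grade.
3. *48 hours or longer.* Here the definitions leave gaps. Two of the four effects have no clear grade.

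Next, does anything elsewhere repair this? The worst-severity rule in Section VI.D selects among several episodes in one patient and does not grade a single episode. Section VI refers to a separate SAP, but analysis rules act on grades that the investigator has already assigned. No adjudication of grades is described.

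Finally, I tested two partial repairs:

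- *Highest grade met, with nothing else changed.* This sends case 1 to Moderate. Case 2 stays Mild, because that is the only definition it meets.
- *Mild redefined by effect, with the other grades unchanged.* Under 48 hours, marked limitation without intervention and more than mild discomfort without limitation both lose their grade. A highest-grade rule cannot grade an event that meets no definition.

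On scale, the plan is for up to 40 subjects. At full enrolment, one subject whose worst grade changes moves a row of the safety-set table by 1/40 = 2.5 percentage points. How many subjects would move cannot be derived.

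**The case against.** The strongest reply is that investigators grade by judgement. Moderate is the grade that names mild to moderate limitation, and a sensible investigator would choose it. One might likewise treat the intervention clause in Severe as descriptive and grade a short, markedly limiting event Severe. This may often happen, but the text tells investigators to use these definitions and gives no order of precedence.

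The reply does defeat a stronger reading. A reader might infer that the severity tables do understate harm. The documents show only that they can, since an event meeting both definitions may correctly be graded Moderate.

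Other limits also stand:

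- The criterion is that no intervention is *required*. A reader might extend the point to all untreated events, but one that needed therapy and did not receive it is not Mild.
- Seriousness is assessed separately ("Each AE will also be independently judged by the investigator in terms of seriousness"). Event counts, relatedness and discontinuations also do not depend on the grade.
- Section III.C records start and end dates and any treatment required, and Section VI.D lists all events. Short events graded Mild can be found afterwards. Limitation of activity is not among the items listed there, so they could not necessarily be regraded from the listing.
- A reader might infer that the ambiguity favours the active device. Section III.K blinds subjects, site staff and sponsor to the randomised assignment, and nothing in the documents points to a difference between arms.
- No adverse event table by site is planned, and Section VI.E says that there is no formal hypothesis testing. Differences between sites are possible but not shown.

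**Conclusion.** The defect is real but minor. On the literal wording of Section X.A, short duration without need for intervention is enough for Mild. This creates an overlap with Moderate that has no tie-break, and it leaves short, markedly limiting events with Mild as their only grade. The severity summaries can therefore understate severity or be graded inconsistently. Because Section IX names severity, the ambiguity also reaches the review on which suspension may rest, though that review covers incidence as well and uses no grade cut-off.

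The conclusion rests on reading the definitions as written and on the absence of any precedence rule in the documents. It does not rest on an assumed share of short events that limit activity; any such share would be a guess.

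**What to change.** In Section X.A:

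1. Remove duration as a sufficient condition for Mild. No information is lost, because start and end dates are already recorded under Section III.C.
2. Reconcile all three definitions on effect and limitation of activity so that every event fits a grade. Two cases need an explicit home: marked limitation where no intervention is required, and more than mild discomfort without limitation.
3. Add a sentence stating that an event meeting more than one definition takes the highest grade met.

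All three steps are needed, since neither partial repair tested above is enough. The cost is an edit to three definitions, one added sentence and an instruction to sites, handled as an amendment under Section IV.M. No visit, procedure or sample size changes. The downside is that the severity table may look slightly less favourable.
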